2.2 Secondary Objective(s)

Secondary endpoints will include a longitudinal comparison of metabolic and serological analysis (specifically measures of glucose and insulin homeostasis); the level of cognitive impairment as defined by neuropsychological testing. Neuropsychological testing measures will include the Quick Dementia Rating Scale (QDRS), Clinical Dementia Rating (CDR) score as estimated by the QDRS, the Alzheimer's Disease Assessment Scale (ADAS-Cog12), the Mini-Mental State Examination (MMSE), and the Montreal Cognitive Assessment (MoCA).

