CLINICAL TRIAL PROTOCOL: NE3107-TRP-001

Study Title: A Phase II Open-Label Study for the Use of Anti-Inflammatory, Insulin-Sensitizing NE3107 for Treatment of Cognitive Decline Due to Degenerative Dementias

Study Number: NE3107-TRP-001

Study Phase: 2

Product Name: NE3107 (17a-ethynyl-androst-5-ene-3b,7b,17b-triol)

IND Number: 159271

Indication: Degenerative Dementias

Investigators: Principal Investigator: **[name], M.D., F.A.A.N.**
Sub-Investigator: [name], M.D.

Sponsor: The Regenesis Project

Sponsor Contact: [name]

Sponsor's Legal Representative: [name], ND, JD
[name]
[name]

Medical Monitor: [name]

Original Protocol:	11/04/2021
Amendment 1:	Version 2, dated 12/17/2021

Confidentiality Statement

This document and its contents are the property of and confidential to [name] Inc. dba The Regenesis Project. Any unauthorized copying or use of this document is prohibited.

SYNOPSIS

Sponsor: [name] MD Inc., dba The Regenesis Project

Name of Finished Product: NE3107

Name of Active Ingredient: 17a-ethynyl-androst-5-ene-3b,7b,17b-triol

Study Title: A Phase II Open-Label Study for the Use of Anti-Inflammatory, Insulin-Sensitizing NE3107 for Treatment of Cognitive Decline Due to Degenerative Dementias

Study Number: NE3107-TRP-001

Study Phase: 2

Primary Objective(s):

Primary endpoints will involve a comparison of neurophysiological health as evaluated by multi-modal brain MRIs obtained at baseline and post-intervention termination (3 months).

Secondary Objective(s):

Secondary endpoints will include a longitudinal comparison of cognitive functioning as well as serological inflammatory markers and glucose and insulin homeostasis.

Study Design:

The present open label study is designed to evaluate the potential efficacy of NE3107 among patients with degenerative dementias through neuroimaging, cognitive performance testing, and serological measures of insulin resistance.

Study Population:

Approximately 25 participants are planned to be enrolled in this study.

Diagnosis and Main Criteria for Inclusion

Inclusion criterion are a diagnosis of cognitive decline due to degenerative dementia and a clinical dementia rating (CDR) score of 0.5 or 1.

Test Product; Dose; and Mode of Administration:

NE3107 20mg BID

Duration of Treatment:

The duration of active intervention will be three (3) months.

Pharmacokinetic Variables:

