3 INVESTIGATIONAL PLAN

3.1 Overall Study Design and Plan

The present study is designed as a Phase II, open-label study of patients with dementia to evaluate potential efficacy of NE3107 using serological measures of insulin resistance, cognitive performance testing, AD biomarkers, and neuroimaging endpoints. Baseline and outcome measures in this study utilize validated tests that are appropriate for repeated measures which are not affected by practice effects. Advantages of this study include the fact that the neuropsychological testing instruments and advanced MRI imaging protocols that have been in routine clinical deployment provide for a high degree of availability and reliability for diagnosis and for monitoring change of status. The study population is sufficiently broad and the conditions of interest are sufficiently prevalent so that recruitment of the projected numbers of participants is not a limiting factor.

The duration of treatment is 3 months. The rationale for 3-month administration is to allow sufficient time for detectable change to occur. To minimize risk, participants will be called within 24 hours following initiation of the drug and weekly thereafter, as well as attend monthly visits the principal investigator to evaluate for safety and tolerability of the study intervention. Mild, moderate, and severe adverse reactions will be reported on an ongoing basis. Previously observed adverse reactions are listed in Table 22 of the Investigator's Brochure. Participants will be discontinued if they have moderate or severe adverse reaction ratings according to the ICH SAE E2A.

(See Appendix 1, Study Events Table.)

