All participants will be administered the NE3107 and instructed to maintain a consistent daily dosage of 20 mg BID for the three-month active intervention period. Primary endpoints will involve a comparison of neurophysiological health as evaluated by multi-modal brain MRIs and neuropsychological testing obtained at baseline and post-intervention termination (3 months) (See 2.1: *Primary Outcomes* and 2.2: *Secondary Outcomes* for detailed descriptions of the MRI modalities and neuropsychological tests, respectively). Additional procedures include blood and serum samples to be collected at baseline and completion to ensure participant safety and effect of NE3107 on laboratory values (See 6.6.1 *Laboratory Parameters*).

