6.6 Clinical Laboratory Tests

6.6.1 *Laboratory Parameters*

Participants will be in a seated or supine position during blood collection. Clinical laboratory tests (to be collected at baseline, 2 weeks, 4 weeks, 8 weeks, and completion) include the following:

Collected at Baseline and Completion:

Hematology:

- Complete Blood Count with Differential
- Hematocrit (Hct)
- Hemoglobin (Hgb)
- Hemoglobin A1c
- Mean corpuscular hemoglobin (MCH)
- Mean corpuscular hemoglobin concentration (MCHC)
- Mean corpuscular volume (MCV)
- Platelet count
- Red blood cell (RBC) count
- White blood cell (WBC) count with differential

Inflammatory Markers:

- Appearance
- Chlamydia pneumoniae serology (IgG/IgM)
- TNF (tumor necrosis factor)
- Cytokine Panel 13
- hsCRP (highly sensitive c-reactive protein)
- ESR (erythrocyte sedimentation rate)
- HSV (herpes simplex virus serology, IgG/IgM)
- CMV (cytomegalovirus serology, IgG/IgM)
- Helicobacter pylori - breath test
- Lymphocyte Subset Panel 4: CD4 & CD8
- Vasoactive intestinal peptide

Serum Chemistry:

- Albumin (ALB)
- Alkaline phosphatase (ALK-P)
- Alanine aminotransferase (ALT; SGPT)
- Amylase
- Aspartate aminotransferase (AST; SGOT)
- Blood urea nitrogen (BUN)
- Calcium (Ca)
- Carbon dioxide (CO₂)
- Chloride (Cl)
- Creatinine
- Creatine kinase and subtypes
- Gamma-glutamyl transferase (GGT)
- Globulin
- Glucose
- Lactate dehydrogenase (LDH)
- Lipase
- Phosphorus
- Potassium (K)
- Sodium (Na)
- Total bilirubin
- Direct bilirubin
- Total protein
- Triglycerides
- Troponins
- Uric acid
- Zinc
- Ethanolamine phospholipids

- TGF -b1	- Ethanolamine plasmalogens
- Alpha Melanocyte stimulating hormone	- DHA ethanolamine phospholipids
- Beta Melanocyte Stimulating Hormone	- Choline phospholipids
- C4A	- Choline plasmalogens
- ACTH, Plasma (Adrenocorticotrophic hormone)	- DHA choline phospholipids
- Anti-gliadin antibodies	- Dietary fatty acids (omega-3, omega-6, omega-9, OA, LA, AA)
- VEGF	- Iron
- Gastrointestinal tract acids (GTAs)	- Methyltransferase/choline system
- MMP-9	- Phosphatidylethanolamines
- Quantitative immunoglobulins	- Phosphatidylcholine
- Lyme Antibody	- Sphingomyelins
- Bartonella quintana antibodies	- Ceramides
Urinalysis, complete	- Homocysteine
- Glucose	- Elongase 5 activity
- pH	- Peroxisomal function
- Bilirubin	- DHA, EPA
- Ketones	- Triacylglycerols
- Nitrite	- Cholesterol total (Fasting)
- Uric acid	- HDL (Fasting)
- WBC, RBC, epithelial cell count	- LDL (Fasting)
	-

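### The secondary endpoint on insulin homeostasis has no insulin assay in any of the five laboratory lists reviewed, and no insulin-resistance index is defined

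*Combined protocol and SAP*

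**What the plan says.** Three places make insulin homeostasis part of a secondary endpoint. Section 2.2 reads "Secondary endpoints will include a longitudinal comparison of metabolic and serological analysis (specifically measures of glucose and insulin homeostasis". The synopsis reads "Secondary endpoints will include a longitudinal comparison of cognitive functioning as well as serological inflammatory markers and glucose and insulin homeostasis". Section 9.5.2 repeats the wording of 2.2 and then prescribes paired-samples t-tests for each secondary endpoint, changes in serological markers included.

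Two places describe insulin resistance as a means of judging efficacy. The study design paragraph of the synopsis names "neuroimaging, cognitive performance testing, and serological measures of insulin resistance", and section 3.1 says the study will "evaluate potential efficacy of NE3107 using serological measures of insulin resistance, cognitive performance testing, AD biomarkers, and neuroimaging endpoints".

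For the measurements themselves, section 6 speaks of "blood and serum samples to be collected at baseline and completion to ensure participant safety and effect of NE3107 on laboratory values" and sends the reader to 6.6.1. That section opens with "Clinical laboratory tests (to be collected at baseline, 2 weeks, 4 weeks, 8 weeks, and completion) include the following" and gives three lists: one headed "Collected at Baseline and Completion", one for weeks 2, 4 and 8, and one for coagulation before lumbar puncture. Sections 7.1 and 7.5 each give a further list of blood tests for baseline and follow-up. Section 3.1 also refers to a schedule of events: "See Appendix 1, Study Events Table".

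**The concern.** A paired t-test needs a named variable measured at baseline and again at completion. For the insulin part of this endpoint the plan names no analyte, index, unit or formula. By contrast, 9.5.2 gives the content and scoring of the ADAS-Cog, MMSE, MoCA and QDRS. The main list in 6.6.1 is also very detailed and goes as far as elongase 5 activity and Bartonella quintana antibodies, yet insulin is not on it.

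Two things are at stake.

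- **The measurement.** If orders are written from these lists, no pre-dose insulin value will exist. Section 6.6.2 describes no retained serum from which one could be recovered once dosing has begun. The trial would then lose a direct measure of insulin sensitivity for a drug that its own title calls insulin-sensitizing.
- **The prespecification.** If insulin is measured under some other instruction, the index is still not fixed in advance. It could then be chosen after the data of an open-label, single-arm study have been seen.

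**Working it through.** This is a comparison of what the endpoint needs with what the lists name, followed by a short count.

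**Step 1: the lists.** Each laboratory list in the text reviewed was read for insulin, C-peptide and the related metabolic analytes.

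| List | Insulin or C-peptide | Glucose | HbA1c | Cholesterol, HDL, LDL, triglycerides |
|---|---|---|---|---|
| 6.6.1, baseline and completion | not named | named | named | named |
| 6.6.1, weeks 2, 4 and 8 | not named | named | named | named |
| 6.6.1, before lumbar puncture | not named | not named | not named | not named |
| 7.1, baseline | not named | not named | not named | not named |
| 7.5, follow-up | not named | not named | not named | not named |

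Insulin or C-peptide is named in 0 of 5 lists. Glucose and HbA1c are each named in 2 of 5, which covers 2 + 3 = 5 time points: baseline, weeks 2, 4 and 8, and completion.

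**Step 2: the index.** HOMA is expanded in the list of abbreviations. No endpoint, time point, formula or analysis uses it. Sections 2.2 and 9.5.2, where an index would be defined, define none.

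**Step 3: pairs available for the t-test.** The inputs are from section 9.2: 25 enrolled and 20% attrition.

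- The plan's own figure is reproduced: 25 × (1 − 0.20) = 20 completers.
- Glucose and HbA1c: about 20 baseline and completion pairs.
- Insulin, if orders follow the five lists: 0 baseline values, so 0 pairs.

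**Step 4: size of the remedy.** One added assay at baseline and one at completion gives 25 + 20 = 45 assays at the planned attrition, and at most 25 × 2 = 50 with none. Section 5.7.2 already requires a fast of at least 8 hours before bloodwork, so the samples would be suitable for fasting insulin.

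**The case against.** The strongest objection is that the evidence is incomplete. Section 3.1 points to Appendix 1, a natural place to list assays, and that appendix was not in the text reviewed. The main 6.6.1 table is broken and ends in an empty bullet. Nor are the lists closed. The lead-in to 6.6.1 is worded as inclusive, and 3 of the 11 blood items in 7.1 and 7.5 (thyroid hormone panel, creatinine clearance, mitochondrial function) are not named in 6.6.1. Under 6.6.2 the study physician writes the orders, so insulin could be requested outside the lists.

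All of this stands. A reader might infer that insulin will not be measured, or that no data source for it exists. The documents do not support that; they show only that none is named where the endpoint and its laboratory tests are described.

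A second objection is that an insulin-resistance surrogate could be derived from the listed fasting glucose and lipids without an insulin assay. That is possible, so it would be too strong to say that this part of the endpoint cannot be assessed at all. But no such surrogate is specified, and it would not be a direct measure of insulin.

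A third objection concerns weight: this is one component of a secondary endpoint in an uncontrolled study of about 25 people. That is fair and limits the importance of the point. It does not remove it, because a pre-dose value that was never taken may be unrecoverable and the correction is small.

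The missing index does not depend on Appendix 1. Even if the schedule lists insulin, 2.2 and 9.5.2 would still leave the test variable undefined, and the schedule would still need to be reconciled with 6.6.1, 7.1 and 7.5.

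**Conclusion.** The point holds in a limited form. Insulin homeostasis or insulin resistance is presented as an efficacy measure in four places (synopsis, 2.2, 3.1 and 9.5.2), but 0 of the 5 laboratory lists reviewed name insulin or C-peptide, and 0 insulin-resistance indices are defined.

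The consequence for the measurement is conditional. If orders follow these lists, there are 0 insulin pairs against about 20 for glucose and HbA1c, and the insulin part of the endpoint cannot be tested directly. This assumes that Appendix 1 and the damaged part of 6.6.1 do not list insulin, that the physician does not order it separately, and that attrition is the planned 20%. The lack of a named index follows from the text of 2.2 and 9.5.2 and needs none of these assumptions.

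Glucose, HbA1c, lipids and inflammatory markers remain assessable, and the primary MRI endpoints are not touched. Confidence is moderate, mainly because Appendix 1 could not be checked.

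**What to change.** 1. Check whether Appendix 1 lists insulin.
2. If it does not, add fasting insulin to the 6.6.1 list headed "Collected at Baseline and Completion". In either case show it in 7.1 and 7.5, so that the lists and the schedule agree.
3. Name one insulin-resistance index with its formula in 2.2 and 9.5.2, for example HOMA from the same fasting sample or another index that the sponsor prefers, and make it the variable for the paired test.
4. If insulin will not be measured, remove the insulin homeostasis and insulin resistance wording from the synopsis, 2.2, 3.1 and 9.5.2.

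This is a cheap improvement: 45 assays at the planned attrition and at most 50, on fasting draws already required, with no added visit or needle, plus a short amendment. The documents give no assay price, so low cost is an assumption. Removing the wording needs no assays but gives up the direct question about insulin sensitivity.

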In this study, the drug under investigation is NE3107 (17a-ethynyl0androst-5-ene-3b, 7b, 17b-triol). NE3107 is a small, blood-brain permeable molecule with anti-inflammatory and insulin-sensitizing properties. The mechanism of action for NE3107 involves selective inhibition of inflammatory mediators.

This study seeks to measure changes in advanced neuroimaging, CNS biomarkers of Alzheimer's disease, inflammatory serological and metabolic parameters, and cognitive performance measures among participants treated with NE3107.

The dose of NE3107 administered in this study will be 20 mg BID. Nonclinical safety studies and prior clinical trials have not identified a toxicity indicating the need for exploration of dose response. NE3107 dose response for anti-inflammatory and insulin sensitizing activity was not statistically resolved between 2, 5 and 10 mg BID in impaired glucose tolerance subjects in trial HE3286-0102. Neither preclinical data, nor available clinical information suggest an ordered dose response relationship across exposure on key indices of glycemic

control and insulin sensitivity. There has been no indication that NE3107's anti-inflammatory activity could be increased with higher exposures. The dose duration will be 3 months. The rationale for 3-month administration is to allow sufficient time for detectable change to occur. The route of administration for NE3107 will be orally. NE3107 is formulated with common excipients used in oral medications in #2 hard gelatin capsules. NE3107 capsules are stable at room temperature for at least 18 months.

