7.5 Follow-up Visit (Day 90 ± 15)

At the 3-month follow-up visit, the following assessments will be performed and recorded in the participant's source documentation/medical record and on the CRF:

- Vital signs
- Weight
- Concomitant medications
- AEs
- Quick Dementia Rating Scale (QDRS)
- Clinical Dementia Rating (CDR) score, derived from QDRS
- Lumbar puncture to test for AB42 and Tau protein levels
- Advanced brain MRI
 - T1, T2, SWI, Neuromelanin, BOLD, ASL perfusion, DTI-NODDI, MRS of the precuneus
- Cognitive examination including:
 - Montreal Cognitive Assessment (MoCA)
 - Mini-mental Status Examination (MMSE)
 - Alzheimer's Disease Assessment Scale (ADAS-Cog12)
- Blood tests for:
 - Complete blood count + diff
 - Creatinine clearance
 - Thyroid hormone panel
 - Electrolytes
 - Inflammatory markers (hsCRP, TNF α , CD4, CD8, absolute neutrophils)

- Quantitative immunoglobulins
- Total and direct bilirubin
- Hemoglobin
- ProdromeScan blood test for:
 - Phosphatidylethanolamines
 - Choline
 - Mitochondrial function

Note: NE3107 was not teratogenic in rat and rabbit safety studies. Sexually active male and female patients on study should continue using barrier method contraception for 72 hours (three days) after the last dose of NE3107 (terminal plasma t1/2 6-8 hours). The outcome of any pregnancy conceived by a patient on study will be followed to term and the results (normal or detailed description of abnormalities) will be collected as part of the study data and reported to the primary IND holder (Biovie, Inc.).

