9.5.2 Statistical Considerations for Secondary Endpoints

Secondary endpoints will include a longitudinal comparison of metabolic and serological analysis (specifically measures of glucose and insulin homeostasis); the level of cognitive impairment as defined by neuropsychological testing (QDRS/CDR, MMSE, ADAS-Cog, and MoCA scores). Thresholds for reporting clinically meaningful change will include references to published minimal clinically important differences (MCIDs) for each measure. Paired samples t-tests will be used to statistically analyze each secondary endpoint, including the cognitive measures described below as well as changes in serological markers.

The ADAS-Cog evaluates participants' cognitive abilities. It is composed of 11 parts that measure word recall, object/figure naming, command following, constructional praxis, ideational praxis, orientation, word recognition, test direction recall, spoken language, comprehension, and word-finding difficulty. The ASAS-COG is scored from 0-70 by measuring the errors made in each task, with a score of 70 representing the most severe impairment. A point reduction of 3.1 to 3.8 has been found to be the minimal clinically important difference (Schrag & Schott, 2012).

The MMSE is a 30-point questionnaire that evaluates cognition. The MMSE includes specific tasks that assess orientation, attention, memory, language and visual-spatial skills. MMSE scores range from 0 – 30 possible points; 0-17: severe cognitive impairment, 18-23: mild cognitive impairment, 24-30: no cognitive impairment. A point decrease \geq 3 on the MMSE has been identified as the minimally clinically important difference (Andres, 2019).

The MoCA evaluates frontal-executive functions (e.g., verbal abstraction and mental calculation), language (e.g., confrontation naming, phonemic fluency), orientation (e.g., person, place, date, day of the week, and time), visuospatial construction (e.g., simple figure copy), divided visual attention, and immediate and delayed memory of unstructured information (Nasreddine, Phillips, Bédoré, Charbonneau, Whitehead, Collin, et al., 2005). MoCA scores range from 0-30 possible points; 26 or greater is considered to reflect normal cognitive status.

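### The Synopsis counts inflammatory markers as a secondary endpoint, sections 2.2 and 9.5.2 define serology as glucose and insulin, and no rule fixes which markers are tested or how

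*Combined protocol and SAP*

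**What the plan says.** **Endpoint definition.** The Synopsis, under secondary objectives, promises a "longitudinal comparison of cognitive functioning as well as serological inflammatory markers and glucose and insulin homeostasis". The Introduction agrees, listing "inflammatory serological and metabolic parameters, and cognitive performance measures among participants treated with NE3107" among what the study seeks to measure. Section 2.2 instead describes the serological part as "metabolic and serological analysis (specifically measures of glucose and insulin homeostasis", and 9.5.2 uses the same restriction: "longitudinal comparison of metabolic and serological analysis (specifically measures of glucose and insulin homeostasis".

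**Test.** The same paragraph of 9.5.2 continues: "Paired samples t-tests will be used to statistically analyze each secondary endpoint, including the cognitive measures described below as well as changes in serological markers". No marker is listed there. Section 9.1 assigns efficacy endpoints to an MMRM, and 9.5 refers primary and secondary endpoints to methods for categorical data.

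**Markers collected.** Sections 7.1 and 7.5 give the same five: "Inflammatory markers (hsCRP, TNF α , CD4, CD8, absolute neutrophils". Section 6.6.1, a list of laboratory parameters, has a longer group under its inflammatory heading, including infection serologies and a breath test.

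**Multiplicity.** Section 9.1 describes a fixed-sequence rule within families and claims strong type 1 error control for every test. The only family it names there is neuropsychological testing. In 9.5.1, the promise to correct for multiple comparisons covers imaging analyses.

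**The concern.** These statements cannot all be followed. A reader of the Synopsis expects inflammatory markers to be compared as secondary endpoints. A reader of 2.2 finds only glucose and insulin. A reader of 9.5.2 finds a test attached to an open category.

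NE3107 is presented as an anti-inflammatory agent, so this endpoint lies closest to its claimed mechanism. The trial has no control group (5.1.2) and no blinding (5.5), so naming the markers in advance is the main protection against selecting those that happened to move. Without it, one nominally significant marker could be reported as a secondary efficacy finding, and nothing in the plan would show how many others were tested.

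**Working it through.** **1. The plan's own figure.** Section 9.2 wants 20 completers with 20% attrition: 20 / (1 − 0.20) = 25, as stated. This is not in dispute. The 80% power behind the 20 cannot be reproduced, because no endpoint, effect size or standard deviation is given.

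**2. Marker counts.**
- 7.1 and 7.5: hsCRP, TNF-alpha, CD4, CD8 and absolute neutrophils, so 5.
- 6.6.1: 23 lines as printed, or 22 without Appearance, which looks like a displaced urinalysis item. Ten of the 22 directly follow the heading. The other 12 (TGF-b1 to Bartonella) follow the chemistry column in a disordered two-column table, so placing them under this heading is plausible but inferred.
- The lists are not nested. Absolute neutrophils is not under the 6.6.1 inflammatory heading and is at most implied by the differential count under hematology. Quantitative immunoglobulins is counted in the 22 but is a separate item in 7.1 and 7.5.

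**3. Does another rule close the gap?** A fixed sequence protects the error rate only when the order is fixed in advance. Section 9.1 gives none, and no serology family is defined. The imaging correction does not reach serology.

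**4. Size if the choice stays open.** Inputs: significance level 0.05 (9.1), taken as two-sided because sidedness is not stated; one test per marker or line; no drug effect. For k independent tests, the chance of at least one p<0.05 is 1 − 0.95^k:
- k = 5: 1 − 0.95^5 = 0.226
- k = 10 (only the lines directly under the heading): 1 − 0.95^10 = 0.401
- k = 22: 1 − 0.95^22 = 0.676

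Markers are likely to be correlated, but the documents give no correlations. Simulated paired t-tests with 20 participants and an assumed equal correlation between markers (20,000 replicates per setting) gave:

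| Assumed correlation | 5 tests | 22 tests |
|---|---|---|
| 0.3 | 21% | 58% |
| 0.5 | 19% | 46% |
| 0.7 | 15% | 31% |

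**5. What adjustment costs.** With 20 completers, a paired t-test has 19 degrees of freedom and noncentrality d × √20, where d is the mean change divided by the standard deviation of change. Solving for 80% power, two-sided:
- one marker at 0.05: d = 0.66
- five markers, Bonferroni, 0.05 / 5 = 0.01 each: d = 0.84
- 22 lines, Bonferroni, 0.05 / 22 = 0.0023 each: d = 0.99

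**The case against.** The strongest reply is that 6.6.1 is a collection list, not an endpoint list. Section 6 says blood samples serve participant safety as well as the effect of NE3107 on laboratory values, and nothing declares every line a secondary endpoint. This stands. A reader might infer that the team will run 22 or more t-tests and count infection antibody titres as efficacy results. The documents do not say so; they only fail to exclude it. The 22 is an upper count of collected lines, read from a disordered table.

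A reader might also expand Cytokine Panel 13 into 13 analytes and reach a higher error rate. The number of analytes is not stated, so that figure has no support here.

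Nor do the documents establish that 2.2 removes every inflammatory comparison. Its wording is that endpoints will include the items named, the Introduction makes inflammatory serology an aim, and 9.5.2 tests serological markers. Reading 2.2 as zero markers puts too much weight on one parenthesis.

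Finally, 9.1 does state a multiplicity rule, so testing without adjustment is not the declared plan. But a rule with no order and no serology family cannot be applied to these markers. Independence also overstates the error rate if markers are positively correlated, which is why the ranges above are given.

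None of these replies reconciles the Synopsis with 2.2 and 9.5.2, or says which markers are endpoints.

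**Conclusion.** The concern holds. The Synopsis and sections 2.2 and 9.5.2 define the serological secondary endpoint differently, 9.5.2 tests an unlisted set, and the error control claimed in 9.1 does not hold for serology. The marker or markers supporting the anti-inflammatory claim can be picked after the results are known, and so can the test.

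If five markers are tested unadjusted, the chance of a false positive is about 23%, or 15–21% with assumed correlations of 0.7 to 0.3. If all 22 lines were tested it would be at most about 68%, or 31–58%. Even at a correlation of 0.7, the 22-line reading carries about twice the risk of the five-marker reading and about six times the nominal 5%. These rates are illustrative. They assume two-sided tests at 0.05, one test per marker or line, and correlations that the documents do not supply. The contradiction itself needs no assumption. The Appendix 1 schedule was not in the text reviewed and could not be checked.

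**What to change.** Before any outcome data are examined:

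1. Use one wording for the secondary endpoint in the Synopsis, 2.2 and 9.5.2, saying explicitly whether inflammatory markers are included.
2. Name the inflammatory endpoint set. The default is the five markers already in 7.1 and 7.5. The sponsor may prefer another set, but it must be listed, and 6.6.1, 7.1 and 7.5 must agree on it.
3. Fix one test for these markers and align 9.1, 9.5 and 9.5.2. The paired t-test in 9.5.2 is the most specific statement now in the plan.
4. Either give the order in which the markers enter the 9.1 sequence, or apply Holm or Bonferroni across the set. Naming five markers without this step would still leave about 23%.
5. State that all other lines under the 6.6.1 heading, including infection serologies, are exploratory or descriptive.

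The cost is wording only, with no new data collection. There are two small downsides. The other markers can no longer be reported as secondary efficacy results, and adjusted tests need a larger effect: with 20 completers, detectable d is about 0.84 for five markers under Bonferroni, against 0.66 for a single one.
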